To date, no evidence has been published to correlate meaningful faith and spiritual activities on the physiological health of caregivers. Exposure of an individual to a physical or mental stressor activates their stress response through the sympathetic nervous system (SNS) axis.⁶⁰ The SNS response involves increased heart and respiratory rate and a shift in blood flow delivery toward the heart, brain, lungs, and skeletal muscles at the expense of other organs, thus preparing the host to fight or flee from the stressor.⁶⁰ This project is innovative in that we are proposing to introduce physiological measures of stress response in AA caregivers related to engaging in Faith-HAT which adds promise to advancing the field of caregiving research. We include an ecologically and stress response measure through the use of a wearable wristband. To measure stress, we have traditionally relied on standard questionnaire instruments whose capacity to measure similar concepts across racial/ethnic groups has been problematic.⁶¹⁻⁶⁴ Further, such instruments are subjective, confounded by the participant's willingness to disclose, and are able only to capture stress perception and exposure⁶⁵ and not truly stress response. In this study, we measure both aspects of this construct (exposure/response). Additionally, measuring stress response unobtrusively in the participant's home-setting adds a novel dimension not previously tackled in ADRD. In the essence of moving science forward, we hope that objectively assessing the physiological measures of stress response in caregivers will corroborate (or not) these standard questionnaire instruments and allow scientists and clinicians to precisely tailor and test interventions to improve the health and well-being of caregivers.⁶⁶

(B) Aims

The project will have 3 aims:

Aim 1. Develop a prototype Faith-HAT for AA families living with moderate and severe ADRD.

Brainstorming workshops with a purposefully created design team and at least 15 semi-structured interviews with faith leaders, caregivers, and PLWD will be used to explore capabilities and resources available to support faith-based home activities and the key spiritual and religious practices families and PLWD consider essential, engaging, and meaningful. Results will be used to develop the content of Faith-HAT. Member checking will occur to validate fittingness and readiness of Faith-HAT for testing.

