Aim 2. Test the feasibility and explore preliminary effectiveness of employing Faith-HAT. Our feasibility outcomes include success in recruitment, engagement, and retention in a purposive sample of 30 dyads. Our effectiveness outcomes include: caregiver-reported behavioral problems in PLWD; caregivers' self-reported psychological well-being (stress, burden, depression); and objective physiological measures of stress response (heart rate variability, skin conductance) to be measured at baseline and 12 weeks.

Aim 3. Construct a refined toolbox of meaningful faith-based home activities. Using integration and refinement of quantitative and qualitative data, results from Aim 2 will be matched, compared, and validated with the design team to refine the meaningful Faith-HAT for AA families living with moderate/severe dementia. The goal of this aim is to have materials ready for deployment for a fully powered clinical trial.

(C) Study Designs

Preliminary Studies: My previous qualitative work showed that families view participation in religious activities as a way to promote the physical and emotional health of AA older adults living with ADRD.^{17,41} The results of this study with 18 AA older adults living with ADRD and their family caregivers stressed the importance of religiosity to the well-being of PLWD.^{17,41} In fact, many PLWD were unable to physically attend church to worship as the disease progressed to the later stages, and families were left to come up with meaningful religious activities to do at home with their family member (i.e., singing gospel songs, praying, watching worship on the television).^{17,41} In my current work with the Atlanta-based Ministerial Alliance, we have found that families affected by ADRD do not attend church due to fear of embarrassment and uncertainty about the PLWD's behavior (Alzheimer's Association Research Diversity Grant 18-56229). These findings support the need for further exploration of religions' impact on AA families affected ADRD.

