or video-recorded sermons. We anticipate that families will have up 30 activities to choose from with the average activity length to be 10 minutes. The toolbox will be placed online. Participants will be able to access the toolbox via a tablet computer that will be provided to them. Before testing, member checks will occur with the design team and stakeholders for their feedback on fittingness and readiness for testing of Faith-HAT.

Aim 2. Test the feasibility and explore preliminary effectiveness of employing Faith-HAT. We will achieve this aim by conducting a feasibility clinical trial ($n = 30$). Our feasibility outcomes will include success in recruitment, engagement, and retention. Our effectiveness outcomes will include caregiver-reported perceived change in behavioral problems in PLWD as the primary outcome and caregivers' self-reported perceived psychological well-being (e.g., stress, burden, depression) and objectively measured physiological stress response (e.g., heart rate variability, skin conductance) as the secondary outcomes. We will use quantitative surveys, qualitative interview data, and caregiver diaries to assess psychological well-being and a wearable wristband to assess the physiological wellbeing.

Figure 3. Implementation Matrix

1-Design: A single arm pre-post design will be employed. Participants will be asked to take part in in-person survey and physiological baseline data collection, engage weekly in at least 3 activities from the Faith-HAT with person caring for living with ADRD for **6 weeks**, complete 12 weekly diary entries online through RedCap platform, and provide in-person survey and physiological endline data **immediately post-intervention and at 6-weeks post-intervention**. In addition to qualitative and quantitative measures, tracking of the enrollment and attrition rate will enable us to compute the “feasibility” of the program. Within the framework of a feasibility study,⁷³⁻⁷⁵ 12 weeks is a reasonable amount of time for the behavior toward the use of the Faith-HAT to be adopted and show meaningful effects.

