4- Intervention: The caregiver/PLWD dyad will engage in Faith-HAT for **6 weeks**. They will select activities from Faith-HAT at least 3 times a week. Possible examples of these activities include devotional readings, prayer, music, religious images, and video and audio recorded sermons. Results from Aim 1 will further specify delivery characteristics for Faith-HAT. Faith-HAT will be placed on online, which requires little technical know-how by users. The PI will provide training to participants on how to use the Faith-HAT and online diary on the tablet computer provided by the project. Training and implementation will be monitored with a checklist documenting the participant's ability to use the device, access the toolbox through Brightspace, implement the intervention, and understand the feedback in relation to troubleshooting. The "dose" and frequency of use of the interventions will be calculated by determining the number of days/weeks the intervention was used for **6 weeks**. The quality of delivery of Faith-HAT will be assessed during weekly online diary checks.

5- Study visits: Enrollment, Baseline, and Endline: Once eligible, the PI will schedule a visit with the participating caregiver to consent and enroll, provide training and instruction on Faith-HAT, and obtain baseline data. Baseline caregiver-reported behavioral problems in PLWD; caregivers' self-reported psychological well-being (stress, burden, depression); and objective physiological measures of stress response (heart rate variability, skin conductance) will be collected. Each week for **6 weeks** the dyad will be asked to complete at least 3 activities from the Faith-HAT, and the caregiver will complete 12 weekly diary entries online. At the end of the intervention, the PI will schedule a visit and participants will provide survey and physiological endline data **immediately post-intervention and at 6-weeks post-intervention.** **Figure 3** shows the various measures collected at each visit.

6. Study procedures: **Figure 3** illustrates the project's associated procedures and analytic plan.

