(c) Stress response using a wristband: We propose to use a wristband, a wearable-sensor (i.e., wristwatch), that detects stress reactivity in an ecologically appropriate setting (to overcome the artificial setting of the clinical site), and to collect longer-duration measurement of the physiological signals.⁸⁴⁻⁸⁶ We will use the E4© watch (Empatica, Boston MA) which includes a photo-plethysmography (PPG) sensor for blood volume pulse and heartrate variability (HRV) measurement and a galvanic skin response (GSR) sensor activity as well as an infrared thermopile.⁸⁴⁻⁸⁶ Caregiver participants will be asked to wear the wristband for 24 hours, simultaneously with the ABPM, prior to starting the intervention and again at the end of the intervention. Empatica® has provided validity data for the wristband suggesting a correlation with standard measures of 0.66-0.99, $p=2*10^{-11}$ for skin conductance levels (SCL)⁸⁷ and similar values 0.98-0.99, $p < 2*10^{-7}$ for HRV (time- & frequency- domains).⁸⁸ We hope to find a reduction in caregiver HRV and GSR, signifying reduced stress reactivity, post-intervention.

(d) Qualitative Interviews: A subsample of 15 caregiver participants will be selected for in-depth interviews (1-hour to be held in person, phone, or videoconference) at post-test to further elaborate on feasibility, acceptability, and preliminary changes related to Faith-HAT. (i.e., *How well did using the Faith-HAT go? Did you notice a behavior change in your family member? Did your family member seem comfortable and engaged while using the Faith-HAT? How has your physical and psychological health changed? Have emotions toward caring for your family member changed? Do you feel closer to your family member? Do you have further ideas on additional religious activities that would be effective to include in the Faith-HAT? Are there any changes you would make to the program?*).

7. Data Collection and Analytical plan:

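### The 24-hour wristband recordings, as described, support a change in ambulatory autonomic level, not the reduced stress reactivity the plan would report

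*Combined protocol and SAP*

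**What the plan says.** The Innovation section describes stress response as activation of the sympathetic nervous system when a person meets a physical or mental stressor. It proposes to "introduce physiological measures of stress response in AA caregivers related to engaging in Faith-HAT". Aim 2 makes this physiological response a secondary effectiveness outcome, with HRV and skin conductance as the measures.

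Section 6(c) of Aim 2 describes a wristband that "detects stress reactivity in an ecologically appropriate setting". Caregivers are to "wear the wristband for 24 hours, simultaneously with the ABPM, prior to starting the intervention and again at the end of the intervention". The section hopes for a fall in HRV and galvanic skin response, "signifying reduced stress reactivity, post-intervention".

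The timing of physiological measurement is given in three ways:

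- Section 6(c): before the intervention and at its end.
- Section (B) Aims, Aim 2: the measures are "to be measured at baseline and 12 weeks".
- Aim 2, items 1 (Design) and 5 (Study visits): endline data are taken "immediately post-intervention and at 6-weeks post-intervention", in addition to baseline.

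The dyad is asked for a minimum of three activities a week for 6 weeks. Under Aim 1, the toolbox is anticipated "with the average activity length to be 10 minutes".

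**The concern.** Reactivity is a contrast between a value during or after an identified event and a reference value, so it needs event times. A free 24-hour recording without event times gives levels and fluctuations mixed over sleep, exertion, rest and whatever else happened that day. If the pre-post change in such a recording is labelled reactivity, the report claims something that was not measured. The label would also pass into Aim 3, whose product is meant to be ready for a fully powered trial.

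The change itself is exposed too. There is no control arm, and each time point is a single day. If a caregiver's two recordings fall on different weekdays, or on days with different sleep or exertion, that difference enters the change and could be read as an effect on stress.

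**Working it through.** **1. Definition against procedure.** The Innovation section's definition needs a stressor. Section 6(c) names no stressor task, places no session inside a recording, gives no event marker, and states no rule for turning 24 hours of signal into a reactivity value.

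**2. Could another section supply the times?**

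- Caregiver diary, 6(b): weekly recall of which activities were used and how often. No clock times are requested.
- Dose, item 4: a count of days or weeks of use.
- Surveys, 6(a): chronic illness and medication are recorded before and after, expressly to help interpret the physiological measures. A sleep questionnaire is included, but no log of the recording night is described.
- Quantitative Analysis, 7(a): the mixed models name scores for stress, burden and behavioral problems. HRV and skin conductance are not named.
- Weekday: the diary is fixed to the same day each week, but no such rule is given for the recordings.

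None of these fills the gap in the readable text. Figure 3, which the plan cites for measures per visit, procedures and analysis, is not shown.

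**3. Number and timing of recordings.** The intervention lasts 6 weeks, so a visit 6 weeks later falls at week 6 + 6 = 12.

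| Source | Occasions | Number |
|---|---|---|
| 6(c) | baseline, about week 6 | 2 |
| (B) Aims | baseline, week 12 | 2 |
| Aim 2, items 1 and 5 | baseline, about week 6, week 12 | 3 |

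The Compensation section's total is 3 × $25 + 12 × $5 = $75 + $60 = $135, which reproduces the stated figure and implies one paid endline. Two paid endlines would give 4 × $25 + $60 = $160. A third recording without event times would not change step 1.

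**4. What one day per time point adds.** Let s be the SD of a caregiver's day-to-day variation in a 24-hour summary; the documents give no value. Assume independent days and 30 caregivers with both recordings. The difference of two single days carries variance 2s², so day-to-day variation contributes s × √(2/30) = 0.26s to the standard error of the mean change. If a share f of caregivers has a shift d in the same direction between recordings (for example from weekday), the mean change is biased by f × d, and a larger sample does not reduce that. The documents give neither f nor d.

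**5. Session overlap.** This bears only on an acute response to a session. Assume 10 minutes per session, at most one session a day, and a recording on a random day during the intervention.

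| Sessions per week | Chance the day holds a session | Expected dyads of 30 |
|---|---|---|
| 3 (minimum) | 3/7 = 43% | 12.9 |
| 5 | 5/7 = 71% | 21.4 |
| 7 | 7/7 = 100% | 30 |

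One session is 10/1,440 = 0.7% of a recording. At the minimum dose, the share of the week is 3 × 10/10,080 = 0.3%. A recording made after the intervention need contain no session.

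**The case against.** The strongest reply is that the plan's physiological question is change across the programme, not response during a session. The Aims, the visit schedule and section 6(c) all compare before with after, and a response related to engagement can naturally mean change after weeks of use. That change can be computed, and it can be set against diary-reported use. The home recordings can also be compared with the questionnaires, which the Innovation section lists as a purpose. This stands. A reader might infer that the wristband data cannot answer anything about Faith-HAT engagement; the documents do not support that.

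Second, 43% might be read as a ceiling on the chance of capturing a session. It is the value at the minimum dose, because the plan sets three a week as a floor. None of the overlap figures bears on a sustained change in level.

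Third, the outcome is secondary, the study is not powered for testing, and the Limitations section disclaims causal inference. This limits the consequence. It does not cure the label, since disclaiming causation says nothing about which quantity was measured.

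Fourth, differences between days are mere noise unless they are systematic, and no direction has been shown. That is correct, so bias is a possibility here and not a finding.

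Finally, the missing Figure 3 may hold detail, so the absence of annotation is a statement about the readable text only.

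**Conclusion.** The point holds as a matter of what is measured and how it is named. From the procedure in the readable text, a pre-post change in 24-hour ambulatory HRV and skin conductance can be derived. Reactivity in the Innovation section's own sense cannot, because no stressor or event is identified in time. The conclusion in section 6(c) about reduced reactivity therefore goes beyond the data.

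The added noise is about 0.26s in the standard error of the mean change, assuming 30 complete pairs and independent days. Any bias has unknown size and direction. The measurement schedule differs between sections and has to be reconciled in any case.

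This is a worthwhile, inexpensive improvement to a secondary outcome of a feasibility study. It is not a flaw that invalidates the trial. The verdict assumes that Figure 3 contains no event log, day-matching rule or definition of the wristband summary measure.

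**What to change.** - Take each caregiver's baseline and endline recordings on the same weekday.
- During each recording, have the caregiver log sleep, exertion and any Faith-HAT session times in a short REDCap form on the tablet the project already provides.
- Use the log to compute HRV and skin conductance over comparable periods, such as sleep and waking time without exertion. State these summary measures in 7(a).
- Report the result as change in ambulatory autonomic level, and remove the reactivity interpretation from 6(c).
- Reconcile the number and timing of recordings across (B) Aims, Aim 2 items 1 and 5, and 6(c), and check the Compensation total against the result.

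A contrast of session against pre-session values within a recording is optional and exploratory. The baseline recording precedes the intervention and has no session to compare, so this contrast would be a new quantity and would not repair the pre-post outcome.

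The cost is protocol wording, one short form per recording, a few minutes of caregiver time, slightly less scheduling freedom, and some extra work to align signals with logged times. These changes need no additional device or visit.

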(a) Quantitative Analysis: Quantitative data will be entered at the time of each interview directly into the dedicated project tablet computer and saved on Emory's secure REDCAP platform. All data entry screens are set up in REDCAP and, where possible, include data delimiters (i.e., skip patterns, valid range limits) to ensure correctness and minimize missing data. Data will be exported into SPSS monthly and syntax run for cleaning, further data verification and file concatenation. Descriptive statistics will be computed through SPSS v 24 to examine patient characteristics. Sex as a biological factor will also be considered as a variable for analysis. While the primary expected products of this work pertain to feasibility, and our study is not powered to conduct formal hypothesis testing, we will perform preliminary analyses with a multilevel modeling framework to assess relative group changes in scores for measures of stress, burden, and behavioral problems of PLWD. Although effect sizes will not be estimated,⁸⁹ general linear mixed models will be applied to account for the repeated measurements for each study participant and a group by time term will be included in the model to gauge trends and direction of effects. In preliminary analyses, descriptive statistics and frequency distributions will be examined to identify outliers and ensure integrity of merged files. For all multi-item scales, internal consistency will be examined using Cronbach's alpha and associated statistics (e.g., item-total correlations, alpha if item deleted). Formal test-retest/inter-rater reliability coefficients will be computed as data are concatenated.

(b) Qualitative Analysis: All interviews will be conducted by the PI, audio-recorded, and transcribed verbatim. To reduce bias, field notes and journaling will be maintained during this phase. Interviews and diary entry data

will be managed in NVivo 12 software. Data collection and analysis will be performed concurrently. Qualitative content analysis will examine manifest and latent content of the diary entry data.⁹⁰ The PI will work with another member of the research team to independently review transcripts and identify codes and the research team will be brought in to resolve any discrepancies among the independently developed codes. Member check will occur to serve as validation of the interpretation.

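### The wristband section gives all HRV measures one favourable direction, downward; short-window HRV would be expected to rise when stress falls, and whole-24-hour SD can move either way

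*Combined protocol and SAP*

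**What the plan says.** Aim 2, item 6(c) (Stress response using a wristband) states the expected result: "We hope to find a reduction in caregiver HRV and GSR, signifying reduced stress reactivity, post-intervention". On recording length it says: "Caregiver participants will be asked to wear the wristband for 24 hours", before the intervention and again at its end. The device validity data cited there cover "HRV (time- & frequency- domains", so more than one family of HRV measures is in view.

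The opening of Aim 2 lists "objectively measured physiological stress response (e.g., heart rate variability, skin conductance) as the secondary outcomes". The Innovation section describes the physiology: "The SNS response involves increased heart and respiratory rate". It does not mention the direction of HRV. It also hopes that the physiological measures "will corroborate (or not) these standard questionnaire instruments".

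Item 7(a) (Quantitative Analysis) estimates no effect sizes. It plans mixed models in which "a group by time term will be included in the model to gauge trends and direction of effects". The outcomes it names are stress, burden and behavioral problems; HRV is not named. Item 6 (Study procedures) says that Figure 3 "illustrates the project's associated procedures and analytic plan"; that figure is not visible in the text available here.

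**The concern.** HRV is not a single quantity. It may be the beat-to-beat variation within a few minutes, the SD of all intervals over a day, or a frequency-domain power or ratio. These need not move together when stress falls. The sentence in 6(c) is the only visible rule for reading HRV, and it makes a fall favourable whichever measure is used.

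If the analysis used a short-window measure, a worsening in caregivers could be read as benefit. The planned comparison of physiology with the questionnaires could then come out the wrong way round. Where a study is not powered for tests and looks at trends and direction, the sign is most of what a reader takes away. The recorded values, the feasibility results, the primary outcome and the sample of 30 dyads are not at stake.

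**Working it through.** **Inputs from the protocol.** A favourable direction of down for HRV and GSR; a 24-hour recording; time- and frequency-domain HRV in scope; stress raises heart rate. The visible text gives no HRV value, SD or effect, so there is no figure of the plan's own to reproduce.

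**Assumptions (none from the documents).** Calm rate 70 bpm (75 in one case); stressed rate 75 to 90 bpm; SD(HR) = 5 bpm at 70 bpm; a day with two states, a share p of it stressed, and no day–night term. Each case is run with SD(HR) constant and with SD(HR)/HR constant.

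**Step 1: short window.** RR = 60000/HR, so by the delta method SD(RR) ≈ SD(HR) × 60000/HR². At 70 bpm this is 5 × 60000/4900 = 61.2 ms. When the rate rises from 70 to h, SD(RR) falls by 1 − (70/h)² under constant SD and by 1 − 70/h under constant relative SD. The sign reverses only if SD(HR) rises by a factor above (h/70)².

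| h (bpm) | Fall, constant SD | Fall, constant relative SD | Rise in SD(HR) needed to reverse |
|---|---|---|---|
| 75 | 12.9% | 6.7% | 15% |
| 80 | 23.4% | 12.5% | 31% |
| 85 | 32.2% | 17.6% | 47% |

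These percentages do not depend on the 5 bpm. More stress lowers short-window SD, so less stress raises it, which is opposite to the direction in 6(c).

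**Step 2: whole 24 hours.** Let S0 and S1 be SD(RR) in calm and stressed periods, and D the difference in mean RR between them. Then

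24-hour SD = √[(1−p)S0² + pS1² + p(1−p)D²], and mean short-window SD = (1−p)S0 + pS1.

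Worked case: p = 0.2, calm 70 bpm, constant SD.
- Stressed at 85 bpm: S1 = 5 × 60000/7225 = 41.5; D = 857.1 − 705.9 ≈ 151.3; SD = √(0.8 × 61.2² + 0.2 × 41.5² + 0.16 × 151.3²) = 83.7 ms.
- Stressed at 75 bpm: S1 = 53.3; D = 57.1; SD = 64.0 ms.

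Each cell gives the value before → after, in ms. The 24-hour columns are for constant SD and constant relative SD; the last column gives both for the short window, in that order.

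| Change | 24-hour SD, constant SD | 24-hour SD, constant relative SD | Mean short-window SD |
|---|---|---|---|
| Stressed rate 85→75, p = 0.2 | 83.7 → 64.0 | 84.7 → 64.6 | 57.3 → 59.6; 59.1 → 60.4 |
| Same, p = 0.5 | 92.0 → 64.1 | 94.2 → 65.8 | 51.4 → 57.3; 55.8 → 59.2 |
| Same, p = 0.8 | 76.1 → 59.6 | 80.3 → 62.3 | 45.5 → 54.9; 52.6 → 58.0 |
| Same, p = 0.9 | 63.1 → 56.8 | 68.7 → 60.1 | 43.5 → 54.1; 51.5 → 57.6 |
| Same, p = 0.95 | 54.0 → 55.2 | 60.7 → 58.7 | 42.5 → 53.7; 51.0 → 57.3 |
| All-day drop, 75/90 → 70/85, p = 0.2 | 73.4 → 83.7 | 76.9 → 84.7 | 50.1 → 57.3; 55.2 → 59.1 |
| Stressed share 0.8 → 0.5, 70/85 | 76.1 → 92.0 | 80.3 → 94.2 | 45.5 → 51.4; 52.6 → 55.8 |

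The first five rows reduce reactivity, meaning the gap between calm and stressed rates. There 24-hour SD falls, except at p = 0.95 under constant SD. The last two rows keep the gap at 15 bpm and change the level or the duration of stress. There 24-hour SD rises.

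**Step 3: second parameterisation.** This adds a day–night component of 60 or 100 ms and uses resting SDs of 30, 50 or 70 ms, rate rises of 5, 10 or 15 bpm, and a stressed SD cut by 30%, by 50% or in proportion to RR (54 settings). Halving reactivity lowers 24-hour SD in all 54 at p = 0.1 and 0.3; it raises it in 2 at p = 0.5 and in 6 at p = 0.7. Cutting the stressed share from 0.7 to 0.5 raises it in all 54. Short-window HRV rises in every setting, but that is built in, because stress is assumed to lower it.

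No frequency-domain index was computed; its direction depends on which index is chosen.

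**The case against.** The strongest reply is that 6(c) speaks of reactivity and of a 24-hour wear. If reactivity means the swing between calm and stressed periods, 24-hour SD should fall, and the calculations mostly agree. This stands. A reader might infer that the stated direction is wrong for 24-hour SD, or fails once stressed periods fill most of the day. The figures do not support that: when only reactivity is cut, the fall persists at stressed shares of 0.5, 0.8 and 0.9. The cases that go against the plan involve the level or duration of stress.

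The short-window sign is also an inference. The protocol says only that heart rate rises; that rate variability does not rise enough to offset this is an assumption. A reader might infer that the Innovation section and 6(c) contradict each other. They do not, because the former says nothing about HRV.

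Figure 3 may name an index and window, so it cannot be said that the plan lacks them. Even so, the sentence in 6(c) would remain unqualified.

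Finally, the sentence expresses a hope, the models in 7(a) do not name HRV, and the Limitations section disclaims causal inference. A reader might infer that a fall in HRV will be reported as benefit or will drive a decision; nothing visible says so. This limits the consequence, but 6(c) still says what a reduction would signify.

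Heart rate may have been meant. In Preliminary Studies, the text calls the Figure 1B result HRV while the caption calls it mean RR and HR. A fall in heart rate would fit the Innovation section. That is a further reason to clarify the wording.

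**Conclusion.** The point holds in a limited form. One downward direction cannot serve unqualified HRV. For short-window beat-to-beat measures the expected direction under less stress is up, unless SD(HR) under stress rises by more than 15%, 31% or 47% for assumed rate rises from 70 to 75, 80 or 85 bpm. For 24-hour SD the plan's direction mostly holds if reactivity alone changes, but not in general if the level or duration of stress changes. The millisecond figures rest on SD(HR) = 5 bpm at 70 bpm and a two-state day, and illustrate sign only. What is affected is the interpretation of one exploratory secondary outcome. It is worth fixing because this is the only visible rule for reading that outcome.

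**What to change.** Replace the sentence in 6(c) with a separate expected direction for each measure:

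- a decrease in skin conductance;
- an increase in short-window beat-to-beat HRV;
- a decrease in 24-hour SD only if reactivity is defined as smaller swings between calm and stressed periods.

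Name the HRV index and the analysis window, or point to Figure 3 if it gives them. Justify a direction for any frequency-domain index. If heart rate was meant, write heart rate. As an editorial matter only, make the label of the Figure 1B correlation in Preliminary Studies agree with its caption (mean RR or HR).

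The cost is one rewritten sentence and one label: no new data, visits or participants. It should be done before the wristband data are examined, so that the favourable direction is not chosen after the results are known.
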